3.4.2 Side-effect diary

Participants will be asked to keep a structured daily side-effect diary. This will include noting the presence (yes/no) and severity (scale 1-10) of side-effects corresponding to the questionnaire items relating to dexamethasone and micronised progesterone use and meal times.

There will also be free text space for any additional side-effects.

3.4.3 Semi-structured patient interviews

A semi-structured qualitative interview [14], will be performed between Day 15-21 over approximately 60 minutes either in person, or by phone. Topics will include patients’ views on their QoL and symptom/side-effect burden, the PROMs used to assess this, and their experience of participation in the trial. Patients will also be asked their opinion on future trial design, acceptability of outcome measures, and randomisation. Approximately 15 patients will be approached to participate in the patient interview.

3.5 Patient pathway and schedule of visits

Please refer to Appendix 3-5 for a breakdown of the patient pathway (Appendix No.3) and Appendix No.4 and No.5 for the Schedule of Visits (Stage 1 and 2), respectively.

3.6 Internal dissemination

3.6.1 Clinical staff

Before, and during, the trial we will raise awareness of the trial with oncologists and neurosurgeons in the Leeds and Liverpool Cancer Centres including seminar presentations to medical, nursing, pharmacy and support staff about brain metastases, their treatment and the challenges of using dexamethasone. We will describe the trial, key eligibility criteria and how to contact the research team. Details of the trial will be made available through secure portals at each trial site.

After the trial completes, results will be reported at local clinical and educational meetings to clinical, research and support staff.

3.6.2 Patients and carers

A patient and public engagement (PPE) representative will lead on the production of information for patients and the public. We will offer to engage with and discuss the treatment of brain tumours, including the role of clinical trials.

Patients and their carers will see the Patient Information Sheet and speak to their oncologist(s) and research nurse(s). They will also be directed to other sources of information e.g. Cancer Research UK and Macmillan websites to ensure they have the information to make informed decisions about their care and to engage the research team with confidence. We will enquire (and record) whether patients and their carers wish to be informed, in an appropriate way and time, of the trial findings.

3.7 External dissemination

During the trial we will use posters/oral presentations at scientific meetings and in journals, as well as social media, to raise awareness amongst clinicians and researchers of the challenges in managing these patients and the role of the current clinical trial.

3.7.1 Clinical and scientific researchers

When the trial findings become available they will be submitted for publication in a high impact, open access scientific journal. We will also submit abstracts to national and international cancer meetings, both general (e.g. Annual NCRI Conference, American Society of Clinical Oncology, European Society of Medical Oncology) and with a specific focus on neuro-oncology (e.g. European Association of Neuro-Oncology, European Association of Neurological Societies, American Association of Neurological Surgeons, British Neuro-Oncology Society).

3.7.2 Patients and public

Increasingly, patient groups attend clinical and scientific meetings so will have access to the trial results, and participate in discussion, through those meetings.

In addition, material will be generated created for use in press releases, blog posts, public magazine articles, social media and other media forms. Presentations that include key patient messages will be planned with key professional groups and organisations and local health systems. The production of any health information by patients and the public will be subject to the rigorous Department of Health Information Standard process to reduce risk.

3.8 Impact

If the current trial is successful we would apply for funding to conduct a definitive Phase II/III double blind, randomised controlled trial of micronised progesterone vs placebo in patients with primary or metastatic brain tumours and symptomatic peri-tumoural oedema that could transform the experience and QoL of patients with brain tumours.

With >12,000 people/year diagnosed with primary central nervous system tumours and >27,000/year affected by metastatic/secondary brain tumours, the overwhelming majority being on dexamethasone, each year up to 40,000 patients in the UK will benefit from micronised progesterone if shown to be an effective dexamethasone-sparing agent. Those who would benefit most are the significant proportion (~19%) of patients who take steroids from the time of diagnosis until death. Because the morbidity and mortality of many primary brain tumours and most with metastatic/secondary is so high, the benefits of reducing dexamethasone related side effects would be disproportionately high.

In addition, the structured dexamethasone dose reduction protocol may also enhance dexamethasone dosing in patients in the control arm. If so, its adoption in the Phase 3 trial has the potential for it to become standard practice and benefit patients with primary and secondary brain tumours in whom there may be scope to use dexamethasone more efficiently.

Finally, through publications and presentations described above and wider dissemination, this study has the potential for more far-reaching and clinically important impact improving outcomes for patients with metastatic brain cancers. The proposed trial will also raise awareness of brain cancer and brain cancer research.

4. PROJECT TIMETABLE

4.1 Trial set up: 8 Months

Secure release of funding; appoint project team; develop protocol; establish Trial Steering Committee (TSC) and Data Monitoring Committee (DMC); IMP preparation (packaging/labelling at distributor and distribution to sites); initiate contractual arrangements between participating institutions/departments; protocol sign off; parameters for monitoring agreed and schedule for meetings confirmed; commence centre set-up and application via IRAS (Integrated Research Application System) for Multi-centre Research Ethics Committee approval and sign off for individual sites; apply for MHRA approval; regular Trial Management Group (TMG) meetings and project oversight; training of site research teams.

4.2 Recruitment

4.2.1 Stage 1 and pharmacokinetic analysis: 6 months

Recruit 6 evaluable patients over a 3-month period; pharmacokinetic data analysis to establish dose for Stage 2.

Pharmacovigilance; data collection; TMG meetings; monitoring accrual progress, identification of problems and intervention as needed.

Central data quality monitoring and site visits as scheduled; independent oversight DMC meeting.

4.2.2 Stage 2: 18 months

Initiate 2nd centre for Stage 2; recruit 36 evaluable patients across both sites over 18 months. Commencement of data collection; pharmacovigilance; TMG meetings; monitoring accrual, identification of problems and intervention as needed; central data quality monitoring and site visits as scheduled; independent oversight, DMC meeting.

4.3 Data Collect & Validation Phase: 3 months

Pharmacokinetic analysis of Stage 2 patients.

Regular TMG meetings; independent oversight, DMC meetings; final data collection and data cleaning; database lock; final analysis.

4.4 Trial Close Down Phase: 1 month

Preparation of study report; upload results to EudraCT (or equivalent post Brexit); end of trial notification; preparing study files for archiving.

Preparation of abstract and manuscript for presentation at national/international meetings and journal submission.

5. PROJECT MANAGEMENT

5.1 Trial Management Group (TMG)

The trial will be managed by a TMG comprising key staff members at SCTRU, together with selected investigators and a PPI representative that will meet monthly throughout the set-up and duration of the study.

5.2 Trial Steering Committee (TSC)

A TSC will be established to provide overall supervision of the trial as per NIHR criteria. The TSC consists of the CI, an independent chairperson, an independent clinician, one independent public members, an independent statistician and observer members of the TMG. The committee will meet prior to the start of the study and convene regularly throughout the duration of the trial.

5.3 Data Monitoring Committee (DMC)

An independent DMC will undertake independent review and will monitor efficacy and safety endpoints. It will comprise an independent chairperson, clinician and statistician and will meet prior to the start of the study and convene 6-monthly throughout the duration of the trial.

6. ETHICS AND REGULATORY APPROVALS

The trial will be submitted to a research ethics committee, the MHRA and HRA for approval during the set up phase of the trial.

7. PATIENT AND PUBLIC INVOLVEMENT

Two surveys through the Brain Tumour Charity Research Involvement Network conducted during the initial concept stage of the trial confirmed support from patients and carers in finding an alternative to dexamethasone. The Marie Curie Research Voices Group was approached

and respondents, who read the proposal with interest, expressed the belief that this is an important study. Likewise, the 2015 NCRI James Lind Alliance Priority Setting Partnerships for neuro-oncology identified dexamethasone use as a question the patient community wants answered (24). Further support to look for an alternative to dexamethasone has come from the NCRI Brain Tumour Clinical Studies Group.

[name] is the PPI representative for the trial and as a co-applicant has been involved with the study design of the trial and writing the lay summary. He will be a member of the TMG and will help with writing the protocol and patient information sheet. He will be involved in writing up of the trial and help develop the dissemination plan.

9. SUCCESS CRITERIA AND BARRIERS TO PROPOSED WORK

9.1 Success criteria

The PROSSPER trial will have been successful if it generates results that underpin a subsequent definitive Phase 3 efficacy trial by

- Defining the oral dose of micronised progesterone required to reach target serum levels
- Confirming the acceptability, tolerability and safety of micronised progesterone, at the selected dose, in this patient population
- Verifying the acceptability and utility of the dexamethasone dose reduction protocol
- Collecting QoL data and PROMs relevant to the symptoms of raised intracranial pressure and dexamethasone side effects
- Demonstrating possible efficacy of micronised progesterone in reducing the dose of dexamethasone needed to control symptoms of cerebral oedema
- Establishing that a Phase 3 trial would be feasible and acceptable to patients.

9.2 Barriers and mitigation

9.2.1 Stage 1 fails to achieve the target progesterone exposure and identify a dose for Stage 2

We have the option to recruit a further 6 patients to Stage 1. If at that point a Stage 2 dose has not been identified, we will discuss with NIHR whether we should recruit additional patients to Stage 1 and modify Stage 2 accordingly, or whether the trial should end.

9.2.2 Stage 2 recruitment is less than anticipated

We have looked at the number of potentially eligible patients and our recruitment plan is conservative. In the event of recruitment slowing we will engage with colleagues, in particular those in the lung cancer and melanoma team; [name] is a senior member of the breast team. In the event of a further “surge” in COVID-19 cases, mandating suspension of recruitment and redeployment of trial staff, we will record all such instances and seek recompense from the NHS or other bodies for whom they are temporarily working. Patients discontinuing for reasons other than progesterone toxicity will be replaced.

9.2.3 The planned Stage 2 dose of micronised progesterone is not tolerable

This is unlikely to be an issue given that progesterone at the doses we anticipate using is well tolerated in other populations. In the event of patients withdrawing due to the toxicity of micronised progesterone they will be replaced, unless this occurs in >20% of patients in which case the combination of progesterone and dexamethasone will be considered unacceptably toxic.

9.2.4 COVID contingencies

Although the development of brain metastases and their management constitutes a medical emergency, the treatment of which would likely not be affected by national guidelines, we recognise that delivery of the trial may be affected by government guidelines and/or NIHR prioritisation of UPH COVID trials. In that event we would discuss mitigation with NIHR.

COVID (and other) vaccinations will be recorded as concomitant medication.

10. WITHDRAWAL OF SUBJECTS

Patients may withdraw from the study at any point, including after giving consent to the trial but before starting treatment; no further data collection will take place.

Patients may discontinue the study for reasons including toxicity, non-compliance, withdrawal of consent or if the investigator judges' continuation not to be in the patient's best interest. Any patient who does not start IMP, will be replaced.

In Stage 1, patients from whom two full pharmacokinetic profiles cannot be obtained will also be replaced

In Stage 2, patients withdrawing due to the toxicity of micronised progesterone will be replaced. The patients replaced will, however, remain evaluable for assessment of tolerability and if such withdrawals occur in >20% of patients the combination of progesterone and dexamethasone will be considered unacceptably toxic.

If at any point throughout the trial, a patient becomes unable to swallow, they should be withdrawn.

Any patients who permanently discontinue IMP should receive the non IMP dexamethasone and other standard of care treatments.

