2. AIMS AND ENDPOINTS

The overall objective is to provide (a) pharmacokinetic data to guide the dosing of micronised progesterone as a steroid-sparing agent for the treatment of brain tumour oedema, (b) evidence of feasibility and (c) preliminary evidence of efficacy to underpin a subsequent definitive randomised controlled trial comparing micronised progesterone and placebo. Prior to a definitive randomised controlled trial several key issues need to be addressed:

- The pharmacokinetics of intermediate-dose oral micronised progesterone require further characterisation,
- The ability to achieve the target steady state plasma progesterone levels requires confirmation as does tolerability in this patient population
- Finally, subsequent trials will greatly benefit from piloting the patient reported outcome measures (PROMs) of QoL, the structured dexamethasone reduction protocol and a preliminary assessment of the efficacy of micronised progesterone as a dexamethasone sparing agent

This information could not be obtained from pre-clinical studies. Whilst well-characterised brain tumour models do exist, our systematic review (2) has shown that no suitable pre-clinical model exists to study peri-tumoural oedema. Furthermore, patients often experience symptomatic

relief within hours of receiving dexamethasone before radiological improvement becomes apparent, which could not be adequately addressed in pre-clinical models. Finally, our approach respects the principles of the 3Rs (Replacement, Reduction and Refinement) in pre-clinical research (60).

This is a two stage trial in patients with brain metastases and symptomatic cerebral oedema. Although we anticipate the study findings to be relevant to patients with primary brain tumours, and that such patients would be included in a future definitive efficacy study, we have excluded them from the current trial because (a) at initial diagnosis patients with high grade primary brain tumours will most likely need early surgical or other intervention and (b) clinical experience suggests that at relapse the dexamethasone dose they require is much more variable.

Stage 1:

Single arm, pharmacokinetic/dose confirmation

Stage 2:

Randomised, double blind, placebo controlled evaluation of micronised progesterone as a steroid sparing agent. Randomisation will be 1:1, with stratification by clinical site (Leeds and Liverpool).

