13.4 Unblinding procedure and documentation

Unblinding will be done via the Interactive Voice Technology (IVR). This is a telephone or web-based application.

All instances of unblinding should be recorded and reported in writing to SCTRUC Prossper team by the local investigator, including the identity of all recipients of the unblinding information.

Details of how a patient can be unblinded will be included in the site file and in the patient's medical records. This will also be covered in the site initiation visit.

Allocation should not routinely be revealed to Prossper personnel, the CI, or members of the research team at the site.

At the end of the study, participants (or their GPs) may request to be unblinded in order to inform ongoing treatment decisions. In such cases, the CI will have a telephone conversation with the participant or GP, to include discussion of the methodological and scientific advantages of maintaining the blind until the data is analysed. If the CI is not available to have this conversation, it will be made by another senior member of the trial team. Following this conversation, if the participant or GP still wishes to be unblinded, a request to SCTRU Prossper team to permit unblinding will be made. If the SCTRU Prossper team agrees, the unblinding will be done by the SCTRU QA Team, such that the CI, trial office team and site research team can remain blind to treatment allocation.

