15.4 Randomisation and Stratification

After ensuring that the patients meet **all** eligibility criteria and has consented to participate in the study, sites will randomise the patient following the instructions described in the PROSSPER work instructions for sites. Once a patient has been randomised, a patient study number will be issued and this should be used in all correspondence.

Stage 2 of the PROSSPER trial will be randomised into two treatment groups: Progesterone arm or placebo arm. Randomisation will be a 1:1 allocation; 18 patients in each group stratified by clinical site (Leeds and Liverpool).

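### The >20% progesterone-toxicity limit names no arm, denominator or operator in a blinded 1:1 trial; if it is applied to pooled counts, placebo patients dilute it

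*Protocol*

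**What the plan says.** Protocol section 2 describes Stage 2 as "Randomised, double blind, placebo controlled evaluation of micronised progesterone as a steroid sparing agent". Section 15.4 adds: "Randomisation will be a 1:1 allocation; 18 patients in each group stratified by clinical site (Leeds and Liverpool").

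The toxicity limit appears twice.
- Section 10 provides for replacement: "In Stage 2, patients withdrawing due to the toxicity of micronised progesterone will be replaced". It keeps those who are replaced in the tolerability assessment. The limit itself then reads: "if such withdrawals occur in >20% of patients the combination of progesterone and dexamethasone will be considered unacceptably toxic".
- Section 9.2.3, on patients who withdraw for progesterone toxicity: "they will be replaced, unless this occurs in >20% of patients". Past that limit the combination counts as unacceptably toxic.

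On who sees allocation, section 13.4 says: "Allocation should not routinely be revealed to Prossper personnel, the CI, or members of the research team at the site". On oversight, section 5.3 says: "An independent DMC will undertake independent review and will monitor efficacy and safety endpoints". The DMC includes a statistician and meets every six months. No section says whether it sees data by arm, and none gives it the 20% limit.

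A second tolerability criterion is in sections 2.2.2.1 and 14.4 (Final analysis): at least 13 of 18 patients tolerating progesterone to the end of the 14-day treatment period, assessed at the end of Stage 2.

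**The concern.** The event counted is withdrawal caused by progesterone, but half of the Stage 2 patients receive placebo. Section 9.2.3 ties replacement to the limit, so someone has to know the rate while patients are still being recruited. The people who would handle replacement are blind. They cannot tell which withdrawn patients took progesterone, and the text speaks only of a percentage of patients. Read literally by that team, the count is withdrawals attributed to the study drug over everyone in Stage 2.

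That denominator includes the placebo arm. Unless as many placebo as progesterone withdrawals are attributed to the study drug, the pooled rate understates the rate on progesterone. The arm could then run well past the sponsor's own limit with replacement continuing. The 13-of-18 criterion is by arm, but it is read only at the end of Stage 2 and so does not act during recruitment.

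**Working it through.** **The plan's own figure.** The 20% limit has no stated derivation. The nearest derived figure is 13 of 18, justified by an 80% interval that excludes 50%. The exact (Clopper-Pearson) lower 80% limit is 0.545 at 13/18 and 0.488 at 12/18, so 13 is the minimum and the figure reproduces.

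**Inputs.** From the protocol: 18 per arm, 1:1, limit >20%, replaced patients kept for tolerability. The protocol gives no withdrawal rates, so these are assumptions:
- p, the true toxicity-withdrawal rate on progesterone: 30%, with 40% as a second case.
- q, the rate of placebo withdrawals attributed to the study drug while blind: 0, 5, 10 or 20%.

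Each calculation is a single look at full enrolment, because the protocol gives no timing.

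**Expected pooled rate.** With 1:1 allocation it is (p + q)/2. At p = 30% this is 15%, 17.5%, 20% or 25% for q = 0, 5, 10 or 20%, which is 0.50, 0.58, 0.67 or 0.83 of the progesterone rate. For the expected pooled rate to reach 20%, p must be 40% − q, that is 40%, 35%, 30% or 20%.

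**Case A: no replacement.**
- By arm: 3/18 = 16.7%, 4/18 = 22.2%. First passed at 4.
- Pooled: 7/36 = 19.4%, 8/36 = 22.2%. First passed at 8. If all withdrawals are on progesterone, 7/18 = 38.9% of that arm does not pass the limit and 8/18 = 44.4% does.
- By arm: P(X ≥ 4), X ~ Bin(18, p). Pooled: P(X + Y ≥ 8), Y ~ Bin(18, q).

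| p | By arm | Pooled, q = 0% | 5% | 10% | 20% |
|---|---|---|---|---|---|
| 30% | 0.84 | 0.14 | 0.28 | 0.43 | 0.71 |
| 40% | 0.97 | 0.44 | 0.60 | 0.73 | 0.89 |

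**Case B: every toxicity withdrawal is replaced until 18 complete per arm, and replaced patients stay in the denominator, as section 10 implies.** With w withdrawals the rate is w/(18 + w) by arm and w/(36 + w) pooled.
- By arm: 4/22 = 18.2%, 5/23 = 21.7%. First passed at 5.
- Pooled: 9/45 = 20.0% exactly, which is not above 20%; 10/46 = 21.7%. First passed at 10.
- Withdrawals before the 18th completer in an arm are negative binomial. By arm, P(W ≥ 5) = P(Bin(22, p) ≥ 5). Pooled, the two arms' counts are convolved and must total at least 10.

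| p | By arm | Pooled, q = 0% | 5% | 10% | 20% |
|---|---|---|---|---|---|
| 30% | 0.84 | 0.27 | 0.37 | 0.49 | 0.73 |

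**Check against the 13-of-18 criterion.** With 4 or 5 toxicity withdrawals among 18 on progesterone (22.2% or 27.8%), the 20% limit is passed. Yet 14 or 13 patients remain, which meets the primary criterion if no one else fails to tolerate treatment. The two rules can give opposite answers on the same data.

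**The case against.** The best defence is that the protocol leaves the denominator open and does not fix it wrongly. The event is progesterone toxicity, the conclusion concerns the combination with progesterone, and the 13-of-18 criterion is judged on the progesterone arm. A by-arm reading is therefore at least as natural. Section 13.4 does not list the DMC among those kept blind, section 5.3 gives it a safety remit, and its tables usually belong in a charter that is not shown. Sections 13.1, 13.3 and 13.4 also let a QA team unblind outside the trial team.

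Much of this stands. A reader might infer that the rule can only be run on pooled data, because everyone running the trial is blind. The documents do not support that: a by-arm check by the DMC is possible. A reader might also infer that placebo halves the rate, but that needs a placebo rate near zero. The protocol gives no such rate, and blinded attribution in ill patients tapering dexamethasone may well be above zero. Nor is this the protocol's only numerical tolerability rule, given 13 of 18. Finally, passing the limit is not said to stop randomisation; section 9.2.3 says only that replacement ends and the combination is judged too toxic.

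What does not stand is that the gap is mere detail. The limit governs conduct during recruitment, and nothing connects it to anyone who can see the arms. Section 13 allows single-case unblinding for listed reasons, and applying this limit is not one of them. The QA-team route serves requests about individuals.

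**Conclusion.** The concern holds as an unassigned and ambiguous rule. Sections 9.2.3 and 10 set a limit on progesterone-toxicity withdrawals without naming arm, denominator or operator, while those who handle replacement are blind. If they apply the literal wording to all Stage 2 patients, the rule is weaker in every scenario computed. At a true progesterone rate of 30% it is passed with probability 0.84 by arm, against 0.14 to 0.71 pooled without replacement or 0.27 to 0.73 with it, for placebo rates from 0 to 20%.

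The loss is large when few placebo withdrawals are attributed to the study drug and modest when the placebo rate approaches 20%. The figures rest on assumed rates and one look at full enrolment. They describe what pooling would do; the protocol does not say that pooling is intended.

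This should be corrected because it bears on safety and is cheap. It does not invalidate the design.

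**What to change.** Leave the sponsor's threshold as it is. In sections 9.2.3 and 10, state that:
- it is assessed on the progesterone arm only;
- the denominator is all patients randomised to progesterone who took at least one dose, including those later replaced;
- the existing DMC assesses it on arm-level data, with the placebo rate alongside, and reports only whether the limit is passed, so that sites, the chief investigator and the trial office stay blind.

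The DMC charter should say when the table is refreshed. At one patient per month at each of two sites, about 12 patients (2 × 6) enter between six-monthly meetings.

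In the same edit, reconcile the limit with the 13-of-18 criterion so that one set of withdrawals cannot both pass the toxicity limit and meet the tolerability endpoint without explanation.

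The cost is wording in two sections, a charter entry, and one unblinded withdrawal table prepared by someone outside the blinded team.
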